4.0 Study-Wide Number of Subjects

We propose a four-center run-in period (n=5) and randomized-controlled trial (n=100) of an evidence-based telehealth intervention for a total of 105 BCS taking AET. Our original accrual goal for the RCT was 75, but due to successful enrollment and additional time for conducting the study, we decided to expand accrual to 100 in order to increase our ability to detect group differences in secondary outcomes.

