10.0 Data and Specimen Banking: Not applicable

11.0 Data Management* and Confidentiality

11.1 Data Analysis

To determine feasibility in a pilot randomized controlled trial (N=100), estimate effect size, and finalize the intervention and study protocol to plan a full-scale, adequately powered efficacy trial.

Power calculation. The primary objective of this pilot study is to demonstrate feasibility, defined as (1) enrollment rate > 50%, (2) retention rate > 70%, and (3) attendance rate \geq 70% (i.e. \geq 70% of participants complete at least 4 of 6 sessions). At the time of the original protocol approval, we

estimated an accrual goal of 80 (75 in RCT and 5 in run-in phase) participants; therefore, the following power estimates are based on that number. We estimated that the enrollment rate will be 60%. If 134 patients are approached and 80 are enrolled, the lower limit for an exact, one-sided 95% confidence interval for the estimated enrollment rate will be 53%. Furthermore, we anticipate that the retention and attendance rates will both be 80%, and with 80 enrolled participants, the lower limit for an exact, one-sided 95% confidence interval for the retention and attendance rates will be 71%. Thus, based on our estimates of the feasibility parameters, the study will demonstrate feasibility of the adherence intervention. We have now expanded our accrual goal to 100 participants, which serves to only increase our power and rates of enrollment, retention, and attendance.

Primary Aim. To examine the feasibility and acceptability of a tailored, small-group, Telehealth intervention (STRIDE) compared to a medication monitoring control for survivors of breast cancer taking adjuvant endocrine therapy.

Hypothesis 1: The study will be feasible, defined by recruitment (enrollment rate > 50%), retention (completion rate of follow-up assessments > 70% of all participants who complete baseline) and attendance (attendance rate of at least 70% of participants completing at least 4 of 6 sessions [60%]).

Hypothesis 2: The study will be acceptable demonstrated by >75% of participants reporting average satisfaction scores greater than the scale's mid-point (Client Satisfaction Questionnaire).

Secondary Aim. To assess effects of the STRIDE intervention on adherence to AET, symptom distress, and satisfaction with AET.

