Hypothesis 1. We hypothesize that participation in the STRIDE intervention will be associated with an increase in adherence and satisfaction with AET and a decrease in symptom distress at 12-weeks compared to the medication monitoring control, and that these improvements will maintain at 24-week follow-up.

Data will be assessed for patterns of missingness⁷² and statistical assumptions. We will conduct mixed effects models with repeated measures data and relevant covariates such social support (MSPSS) and demographic and treatment-related factors (e.g., age, stage, time since AET initiation) as potential covariates. Longitudinal analyses will include all time points and a cross-sectional analysis for each time point. Given that this pilot is not powered to detect statistically significant group differences, we will examine mean differences and sample variability. Effect sizes (Cohen's d) will be calculated for changes in outcomes from baseline to four and eight months, as (Mean change score [intervention arm] – Mean change score [control arm])/SD pooled, where 0.3 indicates a small effect, 0.5 a medium effect, and 0.8 a large effect.⁷³ Effect sizes will be used in a power analysis to estimate the necessary sample size to conduct a full-scale efficacy trial with power >80%. We will also verify the needed sample size based on ability to detect a clinically meaningful difference and references to existing literature.⁷⁴

Exploratory Aim. To assess the effects of the STRIDE intervention on several psychosocial constructs, exploring potential mediator and moderators of the intervention.

Exploratory Hypothesis: We will explore whether participation in the STRIDE intervention is associated with an increase in QOL and medication-taking self-efficacy, and a decrease in distress (anxiety and depression at 12-weeks compared to the medication monitoring control, and whether these improvements are maintained at 24-week follow-up.

We will use the same procedure to assess changes in secondary outcomes in the intervention group. We will explore potential mediation of secondary and exploratory endpoints through changes in beliefs about adjuvant endocrine therapy (BMQ-AET) and/or perceived coping skills (MOCS), as well as self-efficacy for managing symptoms (Self-Efficacy For Symptoms).

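### Section 11.1 says that the larger sample raises the feasibility rates, which it cannot, and leaves limits computed for 80 women; the attendance limit counts controls, who have no sessions to attend

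*Combined protocol and SAP*

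**What the plan says.** Section 8.1 makes enrollment, retention and attendance three of the four parts of the primary endpoint. Section 11.1 defines retention as "retention (completion rate of follow-up assessments > 70% of all participants who complete baseline" and attendance as "attendance rate of at least 70% of participants completing at least 4 of 6 sessions"; the enrollment threshold is 50%.

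The power paragraph in 11.1 states its basis openly: the plan "estimated an accrual goal of 80 (75 in RCT and 5 in run-in phase) participants; therefore, the following power estimates are based on that number". It assumes enrollment of 60%, and retention and attendance of 80% each. From 80 enrolled of 134 approached it gives an exact one-sided 95% lower limit of 53%. From 80 enrolled women it gives a single limit of 71% for both retention and attendance. It concludes that, on these estimates, feasibility will be shown. It then says that accrual has been expanded to 100, "which serves to only increase our power and rates of enrollment, retention, and attendance".

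Section 4.0 gives the current size as 5 run-in women plus 100 randomised. Section 9.2 says that women in the medication monitoring control do not receive the STRIDE sessions.

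**The concern.** An expected rate depends on the women approached and on the procedures. Sample size sets how precisely the rate is estimated. The same paragraph treats 60%, 80% and 80% as fixed planning values, and the documents give no mechanism by which further accrual would raise them.

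The sentence also stands where a recalculation belongs. No section restates the limits for 100 or 105 women, so the reader has only the assurance that everything improves. Redoing the calculation forces the choice of denominator for each criterion, and for attendance the printed denominator includes women who cannot attend. At stake is the planning assurance behind three of the four parts of the primary endpoint.

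**Working it through.** **Inputs.** From 11.1: assumed rates 60%, 80%, 80%; thresholds 50%, 70%, 70%; 80 enrolled of 134 approached; exact one-sided 95% limits. From 4.0: 100 randomised, 105 in total. From 9.2: sessions in the intervention arm only. Assumed: 1:1 allocation. The documents do not state the ratio, but the entries visible in Appendix 30.8 divide almost evenly.

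**Formulas.** The exact (Clopper-Pearson) lower limit L for x of n is the 5th percentile of a Beta(x, n − x + 1) distribution. The chance of clearing a threshold p0 at a true rate p1 is P(X ≥ r), with X ~ Binomial(n, p1) and r the smallest count for which L > p0.

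**The plan's own figures.**
- Retention and attendance, 64/80: L = 71.2%, which matches the printed 71%.
- Enrollment, 80/134: L = 52.2%, not the printed 53%. Approximate methods (mid-p 52.6%, Wilson 52.6%, Wald 52.7%) round to 53%, so the gap is under one point and may come from method or rounding. The text, however, says the interval is exact.

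**Current sample, same assumed rates.** The number approached is 100/0.6 ≈ 167, or 105/0.6 = 175.

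| Criterion | Count | Exact lower limit | Threshold |
|---|---|---|---|
| Enrollment, randomised women | 100/167 | 53.2% | 50% |
| Enrollment, with run-in | 105/175 | 53.5% | 50% |
| Retention, randomised women | 80/100 | 72.3% | 70% |
| Attendance, intervention arm | 40/50 | 68.4% | 70% |
| Attendance, with run-in | 44/55 | 69.1% | 70% |

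For retention the 100 randomised women are the natural base, because run-in women have no 24-week assessment (footnote to the instrument schedule in 9.3).

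**Chance that the limit clears its threshold at the assumed rate.**

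| Criterion | n | Smallest count needed | Chance |
|---|---|---|---|
| Enrollment | 134 | 78 | 70% |
| Enrollment | 167 | 95 | 82% |
| Retention | 80 | 64 | 57% |
| Retention | 100 | 78 | 74% |
| Attendance, intervention arm | 50 | 41 (82%) | 44% |

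The assumed rates do not change between rows. Only the limits and these chances move.

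**The case against.** The strongest reply is that this is a slip of wording: the author meant power for the three rates, and power does rise. That part stands. The gain is material, and describing it only as a shift of about one point in the lower limits would understate it. The literal claim about the rates is still wrong.

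Second, the basis of 80 women is disclosed, and on an all-participant denominator the older limits are conservative. This holds for enrollment and retention, whose restated limits still clear 50% and 70%. It does not hold for attendance, because adding controls to the denominator does not describe women who were offered sessions. That fault predates the expansion: with 75 randomised, about 37 or 38 women would have been offered sessions, and 30/37 gives 67.4% and 30/38 gives 65.2%. The expansion improves the attendance limit but does not bring it over 70%.

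Third, section 8.1 states the endpoint as rates above thresholds, with no rule based on a confidence limit. That is correct. A reader might infer that the trial would fail its attendance criterion; the documents do not support this, since an observed 40 of 50 is 80% and meets the criterion as written. What fails is the planning assurance in 11.1, which is argued through the lower limit.

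A reader might also see a contradiction between section 4.0, where the expansion is made "in order to increase our ability to detect group differences in secondary outcomes", and section 11.1: "Given that this pilot is not powered to detect statistically significant group differences, we will examine mean differences and sample variability". There is none. The statement in 4.0 is relative and the one in 11.1 absolute; ability can improve and remain inadequate. Nor does the plan owe a detectable difference for secondary outcomes. It disclaims power and plans effect sizes, and a figure that treats women as independent would sit badly with sessions delivered in groups.

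**Conclusion.** The sentence in 11.1 is wrong about the rates and right about power. The expected rates stay at 60%, 80% and 80%; the chance of clearing the threshold rises from about 70% to 82% for enrollment and from about 57% to 74% for retention. The printed limits belong to a superseded sample. Correcting them leaves the conclusion intact for enrollment (about 53%) and retention (about 72%).

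For attendance the conclusion changes. On the women offered sessions the limit is 68.4%, or 69.1% with the run-in women, instead of the printed 71%. At the plan's own assumed 80% it does not clear 70%, so the unqualified statement that feasibility will be demonstrated is not supported on that component.

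This rests on the plan's assumed rates, on 1:1 allocation, and on independent binomial counts. It does not show that the stated success criteria will be missed, and it does not depend on any conflict between 4.0 and 11.1.

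**What to change.** In the power paragraph of 11.1:

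1. Delete the part of the last sentence that names the three rates, and say that the expansion improves precision and power only.
2. Restate the exact one-sided 95% lower limits for the current sample: enrollment 53.2% (100/167) or 53.5% (105/175); retention 72.3% (80/100); attendance 68.4% (40/50), or 69.1% (44/55) if run-in women are counted. Name the denominator of each and state the allocation ratio. If the calculation for 80/134 is kept for the record, give it as 52.2%.
3. Qualify the conclusion on feasibility: at an assumed 80% the attendance limit does not clear 70%; at least 41 of 50 is needed, with a chance of about 44%.

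The cost is a few sentences, with no change to design, conduct or data. The downside is that the attendance assurance becomes less favourable. Sections 4.0 and 8.1 need no change on this point.

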8.0 Study Endpoints*

8.1 Primary Endpoint:

The primary endpoint is feasibility and acceptability as measured by participant rates of enrollment (>50%), participant retention (>70%), intervention attendance (>70% attending at least 4 of 6 sessions), and intervention satisfaction (>75% reporting average satisfaction greater than the scale's midpoint).

8.2 Secondary Endpoints:

The secondary endpoints of the study are as follows:

- Changes in adherence between groups on objective MEMS Caps and self-report MARS-5* at 12-weeks and 24-weeks post-baseline (changes in MEMS Caps adherence will be compared across the entire 24-week period).
- Changes in self-reported satisfaction with AET on the CTSQ* between groups at 12-week and 24-weeks post-baseline.
- Changes in self-reported symptom distress on the BCPT* between groups at 12-week and 24-weeks post-baseline.

Secondary endpoints will also be examined using social support (MSPSS*) and demographic and treatment-related factors (e.g., age, stage, time since AET initiation) as potential covariates.

8.3 Exploratory Endpoints:

- Changes in distress levels (HADS*), quality of life (FACT-B*), and medication self-efficacy (SEAMS*) between groups at 10- and 24-weeks post-baseline, as well as potential mediation of secondary and exploratory endpoints through changes in beliefs about adjuvant endocrine therapy (BMQ-AET*), self-efficacy for managing AET symptoms (Self-Efficacy For Symptoms) and/or perceived coping skills (MOCS*). Potential demographic or treatment related moderators will also be explored (e.g., age, type of AET medication, cognitive functioning [PROMIS*]).

*All study instruments are explained in full in Section 9.3.

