9.0 Procedures Involved*

9.1 Study Design

This is a multi-site randomized control trial of a tailored, telehealth intervention (STRIDE) versus standard care plus medication monitoring in up to 105 BCS taking AET (run-in period, n=5; RCT, n=100). To ensure balanced representation between the two study groups, we will stratify randomization by participant level of distress (high vs. low), determined by HADS administered at baseline (Appendix 30.8). A participant will be considered high distress if they answer with a score of ≥ 8 on the HADS. Furthermore, participants who self-identify as part of a minority identifying racial/ethnic group will be offered the opportunity to participate in a qualitative exit interview to gather patient feedback on the study's cultural awareness and relevance. This interview will take approximately 15 minutes.

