Medication Event Monitoring System (MEMS Caps)		To be used throughout the 24-week study period		
Demographics		X		
Medication Adherence Report Scale (MARS-5)		X	X	X
Breast Cancer Prevention Trial Symptom Checklist (BCPT)		X	X	X
Cancer Therapy Satisfaction Questionnaire (CTSQ)		X	X	X
Hospital Anxiety and Depression Scale (HADS)		X	X	X
Functional Assessment of Cancer Therapy (FACT-B)		X	X	X
Measure of Current Status (MOCS)		X	X	X
Beliefs About Medications Questionnaire – Adjuvant Endocrine Therapy (BMQ-AET)		X	X	X
Multidimensional Scale of Perceived Social Support (MSPSS)		X	X	X
Self-Efficacy in Appropriate Medication Use Scale (SEAMS)		X	X	X
Self-Efficacy For Managing Symptoms and Taking AET Questionnaire (Self-Efficacy For Symptoms)		X	X	X
Patient-Reported Outcomes Measurement Information System (PROMIS) – Cognitive Function – Short Form 4a		X	X	X
Client Satisfaction Questionnaire (CSQ)**			X	
Supplemental Medication Diary	To serve as optional as-needed supplement to MEMS Caps (e.g., on vacation)			
Session Rating Form	To be administered during the run-in period after each intervention session			
Intervention Acceptability Form	To be administered during the run-in period at 3-months post-baseline			
Semi-structured Exit Interview	To be conducted during the run-in period at 3-months post-baseline			
Semi-structured Exit Interview	To be conducting during the RCT period after participants complete their participation in the STRIDE program.			

*Run-in participants will not complete a 24-week assessment

**CSQ will be administered to intervention participants only

Screening:

Adapted National Comprehensive Cancer Network (NCCN) Distress Thermometer (Included as part of Study Screening Script in Appendix 30.3 and independently in Appendix 30.17): The NCCN Distress Thermometer is a valid, one-item measure for assessing distress in many cancer populations.⁵⁴ This

measure is scored on a range of 0 (no distress at all) to 10 (extremely distressed), and a score of 4 has been identified as an appropriate cut-off to measure significant distress.⁵⁵ This measure has been modified in this study for the purpose of screening BCS for distress related to taking AET, distress related to breast cancer symptoms/side effects, and distress related to adherence to AET. Participants who indicate a score of ≥ 4 on any of the three distress thermometers will be eligible for participation.

Secondary Outcomes:

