Hospital Anxiety and Depression Scale (HADS):⁶¹ The HADS is a valid self-report measure for assessing anxiety and depressive symptoms among patients in non-psychiatric hospitals.⁶² The 14-item measure contains seven questions to assess depressive symptoms and seven questions to assess anxiety symptoms to distinguish between the two. Patients indicate how they have been feeling on average over the past week. Each item is answered on a scale of 1 to 4. The four possible answer choices vary and adjust for each question.

Functional Assessment of Cancer Therapy-Breast Cancer (FACT-B): The FACT-B is a validated measure used to assess multidimensional quality of life in patients with breast cancer. The measure captures five domains: physical well-being, social/family well-being, emotional well-being, functional

well-being, and additional concerns. Each item is answered on a scale of 0 (not at all) to 5 (very much).⁶³

Self-Efficacy for Appropriate Medication Use Scale (SEAMS):⁶⁴ The SEAMS will be used to measure patient self-efficacy in taking medication. The SEAMS was developed specifically for patients with chronic disease taking long-term medication.⁶⁴ Two factor structures are created: self-efficacy for taking medication under difficult circumstances and under changing circumstances. Each item is answered on a scale of 1 (not confident) to 3 (very confident).

Covariates:

EHR Factors: The following information will be collected from participant EHR: MGH Main vs. Affiliate site, health insurance type, breast cancer stage, treatment (e.g., surgery, chemotherapy, radiation), ET type, time since treatment completion, menopausal status, psychotropic medications, and medical or psychological co-morbidities.

Demographic Questionnaire: Participants will self-report their age, gender, race/ethnicity, marital status, education level, and relationship status.

Multidimensional Scale of Perceived Social Support (MSPSS):⁶⁵ The MSPSS is a validated, reliable scale used to capture levels of perceived social support. The scale consists of 12 items, such as “my family really tries to help me,” and is measured on a 7-point Likert scale.

Potential Mediators

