Potential demographic or treatment related moderators will also be explored (e.g., age, type of AET medication, cognitive functioning [PROMIS]). We will conduct moderated regressions to examine whether a group difference in adherence is moderated by age, social support (MSPSS), employment status, menopausal status, medication type, or other patient/treatment factors. We will explore alternative models using dichotomous outcomes over time.

Findings will inform the planning of an R01 to evaluate the efficacy of a videoconference, tailored intervention in improving ET adherence for BCS. If the current study is not found to be feasible or acceptable, we will have acquired valuable information to proceed in the identification of a patient-centered intervention for BCS. For example, feedback from the final assessment can be used to modify the intervention, such as the addition of a systems-based intervention component if findings show that low health literacy or cost barriers influence intervention effects. Differences in adherence, feasibility, or acceptability based on demographic or clinical characteristics can help determine which individuals may benefit. Ultimately, this project will contribute to the understanding of BCS' needs related to ET. Future studies based on these findings have the potential to influence survivorship care plans, and videoconferencing is a modality that can be widely disseminated. Improved adherence to ET may prevent recurrence and mortality, extending the lives of BCS.

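### The covariates named for the secondary mixed models omit the distress stratum used at randomisation and leave open which MSPSS value would be used

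*Combined protocol and SAP*

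**What the plan says.** On randomisation, Section 9.1 states: "we will stratify randomization by participant level of distress (high vs. low), determined by HADS administered at baseline". The randomisation sheet in Appendix 30.8 lists distress (elevated or not elevated) as the only stratification factor.

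On the secondary-endpoint models, Section 11.1 states: "We will conduct mixed effects models with repeated measures data and relevant covariates such social support (MSPSS) and demographic and treatment-related factors", followed by examples: "e.g., age, stage, time since AET initiation) as potential covariates". Section 8.2 gives the same list: "Secondary endpoints will also be examined using social support (MSPSS*) and demographic and treatment-related factors". Under its Covariates heading, Section 9.3 describes health-record factors, the demographic questionnaire and the MSPSS. Neither the distress stratum nor baseline HADS appears in any of these three places.

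On social support, the schedule in Section 9.3 marks the "Multidimensional Scale of Perceived Social Support (MSPSS") at baseline, 12 weeks and 24 weeks. In the Section 11.1 list, the wording "relevant covariates such social support (MSPSS") carries no time point. Section 11.1 also considers whether the group difference in adherence is "moderated by age, social support (MSPSS), employment status, menopausal status, medication type, or other patient/treatment factors". No section says which MSPSS value serves as covariate or moderator. Section 11.1 plans longitudinal analyses over all time points and a cross-sectional analysis at each.

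**The concern.** There are two separate gaps in the covariate specification.

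The first is the stratum. Stratified randomisation balances the arms on distress, so the arm difference varies less from sample to sample than it would without stratification. A model that ignores the stratum does not know this: it leaves the distress-related variation in the residual and reports a standard error larger than the true one. The estimate is right, but the interval is too wide and the test rejects less often than its nominal level. Section 4.0 gives a better ability to detect group differences in the secondary outcomes as the reason for raising RCT accrual from 75 to 100, so overstating the uncertainty works against the plan's own aim.

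The second is the timing of MSPSS. The other named covariates are facts fixed at entry. MSPSS also has values measured after randomisation, and STRIDE is delivered in small groups. If a follow-up value entered the model and the programme had altered perceived support, the arm coefficient would exclude whatever part of the effect runs through support.

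**Working it through.** **No figure to reproduce.** The documents state no alpha, power or standard error for the secondary mixed models.

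**Inputs for the stratum check.** From the documents: 100 randomised to two arms (Sections 4.0 and 9.1) and one two-level stratum (Section 9.1, Appendix 30.8). Assumed, because the documents do not give them: 50 per arm, 40% in the high-distress stratum, permuted blocks of four, residual SD 1, and a difference g between strata of 0.5, 1.0 or 1.5 residual SDs.

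**Formulas.** With the arms balanced within strata, the stratum cancels from the arm difference, so the true SE = 2 × 1/√100 = 0.200. A model without the stratum has residual variance 1 + g² × 0.4 × 0.6 = 1 + 0.24g², so it reports SE = 0.200 × √(1 + 0.24g²). The stratum's share of outcome variance is 0.24g²/(1 + 0.24g²).

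- g = 0.5: share 0.06/1.06 = 5.7%; SE 0.200 × √1.06 = 0.206
- g = 1.0: share 0.24/1.24 = 19.4%; SE 0.200 × √1.24 = 0.223
- g = 1.5: share 0.54/1.54 = 35.1%; SE 0.200 × √1.54 = 0.248

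**Simulation of the same cases** (4,000 trials each, nominal 5% test):

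| Stratum share | Mean model SE, omitted | Actual SD of estimate, omitted | Type I error, omitted | Mean model SE, included | Type I error, included |
|---|---|---|---|---|---|
| 5.7% | 0.206 | 0.200 | 4.2% | 0.200 | 4.8% |
| 19.4% | 0.222 | 0.200 | 3.1% | 0.199 | 5.3% |
| 35.1% | 0.248 | 0.200 | 1.6% | 0.200 | 4.8% |

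In the middle row (0.200/0.222)² = 0.81: the reported interval has the width that about 81 participants would give with the stratum in the model. If distress is unrelated to the outcome, g = 0, both standard errors are 0.200, and nothing is lost.

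**Limit of this check.** It is a comparison at one visit, so it speaks most directly to the planned cross-sectional analyses. Where the arm effect is estimated as change from a baseline that is itself a response, within-person comparison already removes the constant part of the stratum difference. The cost there is smaller and depends on how far distress predicts change.

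**MSPSS.** Let T be the total effect, a the effect of STRIDE on follow-up MSPSS, and b the slope of the outcome on MSPSS. With no unmeasured common cause, adjusting for follow-up MSPSS gives T − ab; adjusting for baseline MSPSS gives T. The documents supply neither a nor b, so no size can be derived. Large simulated samples with T = 0.40 confirm the direction. Baseline MSPSS returned 0.396 to 0.404 in all 16 scenarios. Follow-up MSPSS returned 0.397 to 0.400 when a = 0, and less whenever a was positive (for example a = b = 0.2: 0.40 − 0.04 = 0.36; simulated 0.357).

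**What is untouched.** Section 11.1 defines Cohen's d as the difference in raw mean change scores over the pooled SD. No covariate enters it, and it is the quantity carried into the next trial's power analysis. The primary endpoint consists of enrolment, retention, attendance and satisfaction rates.

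**The case against.** The covariate list is illustrative: Section 11.1 offers examples and calls them potential covariates, so it does not exclude the stratum. That is correct, but it does not commit to it either. The stratum is the one covariate that the design itself identifies in advance.

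The pilot is stated not to be powered for group differences, and a conservative test in a study focused on estimation does limited harm. This stands, and it keeps the point modest. Interval width still matters when estimates and variability are the stated product.

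A reader might infer that the plan enters follow-up MSPSS and so removes part of the STRIDE effect. The documents do not support that. Repeated measures most naturally describes the outcomes. MSPSS is listed beside age, stage and time since AET initiation, is kept apart from the instruments headed Potential Mediators, and is also a moderator, a role that ordinarily uses the baseline value. Being scheduled at three visits proves little, because nearly every scale is. MSPSS items ask about family, friends and a special person, and no section predicts that STRIDE changes them. A percentage loss of effect would rest wholly on assumed inputs. What stands is an unstated time point.

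A reader might also infer that omitting the stratum biases the arm difference or forfeits the balance gained by stratification. It does neither; only the reported uncertainty is wrong.

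**Conclusion.** The point holds mainly on the stratum. Randomisation is stratified by baseline distress, and the covariates named for the secondary mixed models leave that factor out. The consequence is an overstated standard error and a conservative test, with no bias. In the single-visit illustration the overstatement runs from 3% (0.206/0.200) to 24% (0.248/0.200) as the stratum's share of variance goes from 6% to 35%, and it is nil if distress does not predict the outcome. Those shares, the 40% stratum size and the block length are assumptions.

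The MSPSS part is an open choice to close, not a declared error. Its effect on the mixed-model estimates is unknown and may be zero; restricting MSPSS to baseline is a safeguard that costs nothing if STRIDE leaves perceived support unchanged. Both parts concern the mixed-model secondary estimates only.

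**What to change.** Add one sentence to Section 11.1, and align Section 8.2 with it:

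> The secondary-endpoint mixed models will include the distress stratum as used at randomisation; where MSPSS is used as a covariate or moderator, only its baseline value will be used.

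Take the stratum from the randomisation record rather than recomputing it. Section 9.1 sets the cut-off at 8 on the HADS without saying total or subscale. Section 9.3 scores the 14 items from 1 to 4, so an unrescaled total could not fall below 14. State the score that was actually used.

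No other change to the models is needed for this point. Baseline appears already to be a response in the longitudinal model, so a baseline-outcome covariate need not be added, and the planned mediators can stay as listed.

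The cost is a sentence of text. Both variables are already collected, and no procedure changes.
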